6.2.3 End of trial and follow-up period

The End of Treatment (EOT) visit marks the end of the patient's treatment in the trial, and should be conducted as soon as the patient discontinues trial medication (afatinib), and may occur at any time during the trial. The investigator may discontinue patients due to any of the reasons presented in Section 3.3.4.1.

Doc. No.: U13-1326-02 Trial Protocol Page 55 of 95

Table 6.2.3: 1 End of Treatment (EOT) Visit

	The following must be performed and information recorded in the patient's chart	What to include in eCRF
Physical examination	Physical examination results (see Flow Chart). The evaluation of the ECOG performance score will be performed.	Verify that this physical examination was performed and record results (see Flow Chart).
Disease Assessment	Disease Assessment will be based on the assessment of cancer related symptoms and, if available, radiologic assessments as per standard of care at the site.	Disease Assessment to be included on CRF.
ECG	An ECG may be performed at the discretion of the investigator.	Verify if an ECG was performed.
LVEF (Left Ventricular Ejection Fraction)	Cardiac left ventricular function assessment by either ECHO or (MUGA) only for patients with cardiac risk factors and those with condition that can affect LVEF, at the discretion of the investigator and in accordance to the current standard of care.	Verify if an ECHO (or MUGA) was performed.
Safety Laboratory Testing – Optional	Hematology, and Biochemistry examination. See Section 5.2.3 for recommended safety laboratory evaluations. Laboratory testing is optional at this visit and may be performed at the discretion of investigator and in accordance to the current standard of care. Refer to Section 5.2.3 for a list of recommended safety laboratory tests. If performed as part of a safety evaluation visit, the test results must be filed or recorded in the patient's chart.	Verify if all recommended safety laboratory testing was performed and that values were acceptable according to the protocol. If not, see Section 5.2.2.1 No lab values are to be recorded on the CRF.
Urine Examination –	Urine examination. (see Section 5.2.3 for recommended urine examinations).	Verify if all recommended safety Urine testing was performed.
Optional	Urine testing is optional at this visit and may be performed at the discretion of the investigator and in accordance to the current standard of care.	No values from the urine examination are to be recorded on the CRF.
Pregnancy test	β-HCG testing in urine or serum will be performed in females of childbearing potential.	Verify that β-HCG testing in urine or serum was performed and that patient is not pregnant.
Adverse events	Patients should be asked to report any hospitalizations, emergency treatments, or new medications as well as any general health issues that may have surfaced since their last visit. All the information collected should be recorded in the patient's chart. Refer to Sections: 5.2.2 and 5.2.2.2 for protocol specific requirements regarding the collection and reporting of adverse event information.	All relevant AEs and all SAEs.

Table 6.2.3: 1 (continued) End of Treatment (EOT) Visit (Page 2 of 2)

	The following must be performed and information recorded in the patient's chart	What to include in eCRF
Compliance	Collect all unused or partially used and empty bottles of afatinib (Giotrif®) from the patient. Check number of tablets remaining and check that trial medication taken correctly.	Record if the patient took the medication according to the protocol. This information should be captured on the Termination of Trial Medication eCRF.
Concomitant Medications	Patients should be asked to report any concomitant drug use (including, but not limited to,: non-prescription medications, anaesthetic agents, homeopathic/herbal remedies and dietary supplement preparations).	No concomitant medications will be recorded on eCRFs.
Termination of Trial Medication	Document any information regarding the patient's last dose of trial drug and why it was stopped. (e.g., date of withdrawal of consent, lost to follow-up, disease progression) When applicable, every effort should be taken to	Date when the last dose of trial medication was ingested. Reason for discontinuation.
	collect and document information on date of death. Note: any AE which results in death* is considered an SAE.	

^{*} The term "Death" should not be reported as the SAE, it is the outcome of an AE.

6.2.4 Follow-Up

The Follow-up (FU) visit should occur 28 (-7) days after the EOT visit.

Follow-up visits should be scheduled for patients who met the trial withdrawal criteria (see Section 3.3.4). This visit marks the end of the patient's participation in the trial. Patients will not be required to attend the clinic for this visit. The clinic staff will contact the patients or their caregivers by telephone and inquire about any adverse events that might have occurred since the last visit and if applicable follow up on any unforeseen pregnancy during the trial. All concomitant medication should be added to the patient's chart. The Patient Status eCRF will be completed at this time.

Any additional (unscheduled) follow-up visits should be scheduled for patients with unresolved SAEs, AEs, or laboratory abnormalities who have discontinued trial participation. These events must be followed until resolution or until agreement is reached between the local medical monitor and the investigator that further follow-up is no longer required.

Doc. No.: U13-1326-02 Trial Protocol Page 57 of 95

Table 6.2.4: 1 Follow-up (FU) Visit/EOT + 28 Days (-7)

	What to Include in the Patient's Chart	What to include in eCRF
Adverse events	Patients should be asked to report any hospitalizations, emergency treatments, or new medications as well as any general health issues that may have surfaced since their last visit. All the information collected should be recorded in the patient's chart. Refer to Sections: 5.2.2 and 5.2.2.2 for protocol specific requirements regarding the collection and reporting of adverse event information.	All relevant AEs and all SAEs.
Concomitant Medications	Patients should be asked to report any concomitant drug use (including, but not limited to,: non-prescription medications, anaesthetic agents, homeopathic/herbal remedies and dietary supplement preparations).	No concomitant medications will be recorded on eCRFs.
Patient Status	Document any information regarding the patient's status during the planned observation time (i.e., 28 days after the patient's last dose of medication).	Any new anti-cancer medication that the patient has taken since EOT visit.
	When applicable, every effort should be taken to collect and document information on date of death.	Date when the patient completed the planned observation time.
	Note: any AE which results in death is considered an SAE.	Date of death Patient's status

Page 58 of 95

7. STATISTICAL METHODS AND DETERMINATION OF SAMPLE SIZE

Exploratory descriptive statistics of demographic, efficacy and safety data will be presented.

7.1 STATISTICAL DESIGN - MODEL

This is an open-label, multi-centre, non-randomised, uncontrolled, single arm trial designed to evaluate the safety, tolerability and efficacy of the investigational drug afatinib (Giotrif®) in a particular patient population. After the initial screening visit, patients will enter the open-label treatment period with safety visits at approximately every 28 days until the end of the trial.

7.2 NULL AND ALTERNATIVE HYPOTHESES

It is not planned to test any statistical hypotheses with regard to the endpoints described in Section 7.3.2 confirmatory sense since the objective of this trial is to describe the safety of long term use of afatinib (Giotrif®) in this patient population in an uncontrolled manner.

7.3 PLANNED ANALYSES

All analyses will be based on the Treated Set (TS) which includes all patients who were dispensed trial medication and have taken at least one dose of investigational treatment (afatinib).

7.3.1 Primary analyses

Refer to Section 7.3.3 for a description of the analysis of safety and tolerability, the primary objectives of this trial.

7.3.2 Secondary analyses

Progression-free survival

Progression-free survival is the time from start of treatment to the date of disease progression or death, whichever comes first.

For patients with known date of progression:

Progression-free survival [days] = date of progression (or of death if no earlier progression) – (date of start of treatment) + 1

For patients known not to have progressed, i.e., those remaining on trial drug:

Progression-free survival (censored) [days] = date of last contact showing no disease progression or death - (date of start of treatment) + 1.

Patients with unknown progression status or unknown date of progression will be censored at the last contact date, refer to Section 7.4 for more detail.

Kaplan-Meier estimates and 95% confidence intervals for the 25th, median, and 75th percentiles of the survival distribution will be calculated for progression-free survival,

Proprietary confidential information.

Page 59 of 95

using Greenwood's standard error estimate. Kaplan-Meier curves will be produced without confidence intervals.

Tumour response according to investigator's assessment

Each patient will be assigned to one of the following categories:

- 1. Complete response
- 2. Partial response
- 3. Stable disease
- 4. Progressive disease
- 5. Not evaluable for response, reasons to be specified (e.g. early death, tumour assessments incomplete, etc.)

In the case that the tumour assessment was not based on radiological tumour imaging the categories 'complete response' and 'partial response' will be grouped together. Objective Response (OR) is defined as complete and partial responses according to investigator's assessment.

Time to tumour response is defined as the time from the start of treatment to the date of first recorded CR or PR.

The duration of tumour response is the time from first documented CR or PR to the time of progression or death (or date of censoring for PFS).

Patients whose best assessment is stable disease, partial, or complete response will be considered to have achieved disease control. Duration of disease control will be the same as time to progression, but restricted to patients who achieve disease control.

Descriptive statistics will be calculated for the duration of objective tumour response and disease control. Finally, the proportion of patients in each response category will be tabulated, if feasible (confirmation of response not required). Two-sided 95% confidence intervals will be given for the calculated best response rate. Best response is defined as the best individual response from the date of the first administration until the earliest recording of PD, death or end of treatment (as long as no other anti-cancer therapy has been given).

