7.4 HANDLING OF MISSING DATA

Missing or incomplete AE dates are imputed according to BI standards.

- For PFS:
 - If a patient is known to have progressed, but the date of progression is not attainable, the last date when the patient was assessed will be used as date of progression.
 - o If a patient's vital status or progression status is unknown at the follow-up visit, the patient will be censored at the last contact date.

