3. INTRODUCTION

[figure not shown]
As per ICH E9, the purpose of this document is to provide a more technical and detailed elaboration of the principal features of the analysis described in the protocol, and to include detailed procedures for executing the statistical analysis of the primary and secondary variables and other data.

This Trial Statistical Analysis Plan (TSAP) assumes familiarity with the Clinical Trial Protocol (CTP), including Protocol Amendments. In particular, the TSAP is based on the planned analysis specification as written in CTP Section 7 “Statistical Methods and Determination of Sample Size”. Therefore, TSAP readers may consult the CTP for more background information on the study, e.g., on study objectives, study design and population, treatments, definition of measurements and variables, planning of sample size, randomization.

SAS® Version 9.2 or higher will be used for all analyses.

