4. CHANGES IN THE PLANNED ANALYSIS OF THE STUDY

Section 7.3.2 of the CTP describes the “Secondary Analysis” of the efficacy endpoints. It was decided to consider the efficacy endpoints as further endpoints rather than secondary endpoints due to disclosure requirements. Hence this TSAP describes these efficacy endpoints as further endpoints in [Section 5.3 \(Further Endpoints\)](#).

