6.6 HANDLING OF MISSING DATA AND OUTLIERS

Missing or incomplete AE dates are imputed according to BI standards (see “Handling of missing and incomplete AE dates”).[\(1\)](#)

For efficacy data, the following rules will apply:

- For PFS, duration of objective response and duration of disease control, if a patient is **known** to have progressed during the treatment period, but the date of progression is not attainable, the following sequence for imputation of progression date will be followed:
 - Use the date of cancer-related symptoms assessment or visit date in which the progression was recorded (whichever is earliest).
 - If this is missing, the last known visit date or cancer related symptoms assessment date prior to the recorded progression (regardless of the disease assessment result at that visit) will be used.
 - If any such patient has no visit date or cancer related symptoms assessment date recorded at all, the date of first administration of study medication will be used as the date of disease progression.
- For overall survival, if a patient is known to have died (due to any cause), but date of death is not attainable, the last date when the patient is known to be alive will be used as date of death.

For partial treatment discontinuation date, the following logic is applied:

If month and year are known but day is missing, then use date of death if within the same month for a patient who died. Otherwise use last day of the month.

Missing biomarker values will not be imputed.

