10. HISTORY TABLE

Table 10: 1 History table

Version	Date (DD-Mmm-YY)	Author	Sections changed	Brief description of change
Final	24-Apr-2017	[REDACTED]	None	This is the final TSAP without any modification

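### Protocol 7.3.2 censors patients whose progression date is unknown, whereas Protocol 7.4 and SAP 6.6 count a known progressor without a date as a PFS event (minor)

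*Protocol*

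**What the plan says.** **Protocol 7.3.2 (Secondary analyses), PFS.** "Patients with unknown progression status or unknown date of progression will be censored at the last contact date, refer to Section 7.4" for more detail. Two groups are named: those whose status is unknown, and those whose date is unknown. Both are censored.

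**Protocol 7.4 (Handling of missing data), PFS.** "If a patient is known to have progressed, but the date of progression is not attainable, the last date when the patient was assessed" becomes the progression date. A separate bullet censors at last contact only when vital status or progression status is unknown at the follow-up visit.

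**SAP 6.6 (Handling of missing data and outliers).** The rule covers PFS, duration of objective response and duration of disease control. It applies to a patient known "to have progressed during the treatment period, but the date of progression is not attainable". The date is then imputed in three steps:
- First: "Use the date of cancer-related symptoms assessment or visit date in which the progression was recorded (whichever is earliest").
- If that is missing, the last earlier visit or symptom-assessment date.
- If no such date exists at all, the date of first administration.

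**Protocol 7.3.2, duration of response.** It runs from first documented response "to the time of progression or death (or date of censoring for PFS").

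**SAP 3 and 4.** The SAP says that "the TSAP is based on the planned analysis specification as written in CTP Section 7". Its only declared change is this: "It was decided to consider the efficacy endpoints as further endpoints rather than secondary endpoints due to disclosure requirements".

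**The concern.** One patient, known to have progressed but without a date, is censored under one section of the protocol and an event under the next. This is a conflict within the current protocol text; it does not come from the amendment history.

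The direction matters. Someone known to have progressed has, by definition, reached the end of progression-free time. Censoring that patient treats the event as not yet seen and credits further event-free time. Such censoring is informative, and it can only push the Kaplan-Meier curve upwards.

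Protocol 7.3.2 is where PFS is defined, so it is the text most likely to be quoted in a report or table footnote. Protocol 7.3.4 also allows efficacy results to be presented and published once recruitment has ended. What is at stake is a descriptive median, and quartiles, that look slightly better than the data support, or a stated definition that does not match what was programmed.

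**Working it through.** **Step 1. Set the rules side by side.**

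| Patient | Protocol 7.3.2 | Protocol 7.4 | SAP 6.6 |
|---|---|---|---|
| Progression status unknown | Censored at last contact | Censored at last contact | No rule in the visible text |
| Known progressor, date not attainable | Censored at last contact | Event at last assessment | Event at imputed date (progression during the treatment period) |

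The second row conflicts. Could the date phrase in 7.3.2 mean only patients whose progression is itself uncertain? No: that group is already listed in the same sentence as unknown status, so the second phrase has work to do only for known progressors.

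**Step 2. Size of the effect.** The plan gives no PFS assumption, event count or sample-size calculation to reproduce (Protocol 7.6 says the number of patients is not based on one). The following is therefore an illustration.

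Inputs:
- Median PFS m = 11.1 months: the afatinib arm of LUX-Lung 3 (Protocol 2.3). It is not an assumption of this plan.
- N = 481 (Protocol synopsis).
- Exponential PFS; 80% of patients with an event, so 0.80 × 481 = 385 (assumed).
- Share f of progressors without a date: 1%, 2%, 5% (assumed; the documents give none). Of 385 progressors this is about 4, 8 or 19 patients.

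If a random share f of events is censored at the event time, the apparent hazard falls from λ to λ(1 − f). The median becomes m/(1 − f) and the 75th percentile becomes 2m/(1 − f).

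| f | Median (months) | Change | 75th percentile (months) | Change |
|---|---|---|---|---|
| 0 | 11.10 | – | 22.2 | – |
| 1% | 11.1/0.99 = 11.21 | +0.1 | 22.4 | +0.2 |
| 2% | 11.1/0.98 = 11.33 | +0.2 | 22.7 | +0.5 |
| 5% | 11.1/0.95 = 11.68 | +0.6 | 23.4 | +1.2 |

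Censoring at a contact 21 to 42 days after progression, rather than at progression, changes the medians little: 11.22, 11.34 and 11.72. If 10% of PFS events are dated deaths, the 5% case gives 11.6 to 11.7.

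The relative shift 1/(1 − f) does not depend on the median. At f = 5%, a median of 8.0 becomes 8.0/0.95 = 8.4, and 13.6 becomes 13.6/0.95 = 14.3.

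**Step 3. Compare with sampling error.** In simulation with 481 patients, 385 expected events, and a log-log Kaplan-Meier interval with Greenwood's standard error, the estimated median has a standard deviation of 0.72 month. The 95% interval averages about 9.7 to 12.5 months. Coverage of the true median is about 94% to 95% at f = 0 and f = 1%, about 93% at f = 2%, and 88% at f = 5%.

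**Step 4. Does the difference in dating between 7.4 and SAP 6.6 matter?** Counting the undated progressors as events at the prior visit or at the recording visit keeps the median between 11.06 and 11.11 months for every f above. What matters is event against censored, not the imputed date.

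**The case against.** The strongest reply is that the conflict is already settled in practice. The disputed sentence points to 7.4 for detail, 7.4 makes the patient an event, and the final SAP agrees. A programmer would have to ignore both to apply 7.3.2 literally. Disease assessment is due every 28 days and is entered on the case report form, so a recorded progression will usually carry a visit date. This stands as a reason to expect little practical harm. It does not remove the contradiction from the protocol's own definition, and SAP 6.6 covers only progression during the treatment period. For progression recorded later, the visible text that contradicts 7.3.2 is Protocol 7.4 alone. The SAP sections on further endpoints are redacted and may say more.

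Three stronger readings are tempting and are not supported:

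- *The SAP departs from the protocol without declaring it.* On event status SAP 6.6 follows Protocol 7.4, which is itself part of Section 7. No undeclared departure on that question is shown.
- *The conflict carries over unresolved to the duration endpoints.* Protocol 7.3.2 does tie duration of response to the PFS censoring date. But SAP 6.6 names duration of objective response and of disease control, and applies the event rule to both for progression during the treatment period. There the conflict is mainly one of protocol wording.
- *The reported PFS will be materially biased.* The loss of coverage to 88% appears only at an assumed 5% share, and nothing in the documents supports that figure.

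**Conclusion.** The point holds, and it is minor. As written, Protocol 7.3.2 states a wrong rule for known progressors without a date, and it contradicts the section it cites as well as SAP 6.6. If it were applied, median PFS would be overstated by about 0.1, 0.2 or 0.6 month at assumed undated shares of 1%, 2% or 5%. That rests on an exponential model with a median of 11.1 months, and each shift is below the 0.72-month standard deviation of the estimated median.

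The consequence is limited to description. Safety is the primary endpoint, the SAP treats efficacy as further endpoints, and Protocol 7.2 plans no confirmatory test. The difference in dating between Protocol 7.4 and SAP 6.6 has a negligible effect and needs no change on this account.

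**What to change.** Delete 'or unknown date of progression' from Protocol 7.3.2, so that only unknown progression or vital status leads to censoring. The definition then agrees with 7.4 and with SAP 6.6.

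If a further protocol amendment is out of proportion at this stage, add a sentence to SAP section 4. It should say that Protocol 7.4 and SAP 6.6 govern, and that known progressors without a date are always events, dated by the existing SAP 6.6 sequence. Keep that sequence whole, including the fallback to the date of first administration; otherwise a patient with no visit or assessment date would be an event without a date.

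Cost: one deleted phrase or one added sentence, and no new data. No programming changes if SAP 6.6 is already programmed. The protocol route needs the usual amendment approvals; the SAP route needs a new SAP version. The downside is a slightly less favourable PFS than 7.3.2 would give.

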7.3.3 Safety analyses

All treated patients will be included in the safety analysis. In general, safety analyses will be descriptive in nature and will be based on BI standards. No hypothesis testing is planned.

Statistical analysis and reporting of adverse events will concentrate on treatment-emergent adverse events. To this end, all adverse events occurring between first drug intake until 28 days (inclusive) after last treatment administration will be considered 'treatment-emergent'. Adverse events that start before first drug intake and deteriorate under treatment will also be considered as 'treatment-emergent'.

Trial Protocol Page 60 of 95

Frequency, severity, and causal relationship of adverse events will be tabulated by system organ class and preferred term after coding according to the current version of the Medical Dictionary for Drug Regulatory Activities (MedDRA).

Adverse events will be graded according to CTCAE, Version 3.0 (R04-0474).

CTC grades will be applied to laboratory parameters using the current BI oncology standard as detailed in the document 'Conversion of laboratory parameters to CTCAE grades within BI.'

Vital signs, physical examinations, or other safety-relevant data observed at screening, baseline, during the course of the trial and at the end-of-trial evaluation will be assessed with regard to possible changes compared to findings before start of treatment.

